9.1 Delay Graft Function

Delayed Graft Function will be defined as the need for dialysis during the first week after transplantation (with the exception of a single dialysis in the first 48 hours to treat hypervolemia and/or hyperkalemia after surgery. Patients with graft loss due to vascular thrombosis will be excluded.

9.2 CMV infection and disease

- 9.2.1 CMV Infection:** evidence of asymptomatic replication of CMV.
- 9.2.2 CMV Disease:** evidence of CMV infection with related symptoms. CMV disease can be categorized as a syndrome (fever, malaise, leukopenia, or thrombocytopenia) or as an invasive disease with histological evidence.
- 9.2.3 Recurrent CMV disease/infection:** defined as a new episode of CMV infection after documented effective previous treatment (2 weekly negative antigenemia tests).
- 9.2.4 CMV replication:** will be confirmed by detection of CMV pp65 antigen by indirect immunofluorescence in peripheral blood leukocytes. The diagnosis of viral replication is confirmed by the presence of 10 or more positive cells per 200,000 peripheral blood leukocytes in asymptomatic patients or any number of positive cells in the presence of typical symptoms or in recipients with negative serology for CMV.
- 9.2.5 Preemptive strategy:** monitoring of CMV replication will be performed every 15 days between the third and 12 weeks after transplantation. Additional monitoring will be performed for 12 weeks after treatment for acute rejection.
- 9.2.6 Treatment of CMV disease/infection:** Patients will receive standard intravenous ganciclovir (5 mg/kg every 12 hours) corrected for renal function as per package insert recommendations. Monitoring of CMV replication will be carried out weekly. The duration of treatment will be extended by one week after the first negative antigenemia test. Consequently, the minimum duration of treatment will be 14 days. The duration of treatment for patients with invasive disease will be at least 21 days, being extended in the presence of a positive antigenemia test.

10 Statistical planning

10.1 Sample size - main study

Primary outcome: cytomegalovirus infection or disease

For the primary outcome of cytomegalovirus infection, we calculated the sample required to show superiority of the experimental groups (EVR and SRL) over the control (MPA). For this calculation, we considered an incidence of 72% in the MPA group and an expected reduction of 50% (to 36%) in the experimental groups. For a margin of superiority of 0% and power of 90%, the total number of patients would be 42 in each group, considering 20% drop outs.

11 Reference

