1.2 Objective

This study was designed to assess the influence of using SRL or EVR (controlled for their residual blood concentrations) with TAC (reduced residual blood concentrations) compared to MPA (fixed doses) with TAC (standard residual blood concentrations) with regard to efficacy and safety in de novo kidney transplant recipients.

The primary outcome is the incidence of CMV infection/disease, a relevant medical need in the absence of pharmacological prophylaxis due to its morbidity and costs incurred by the public health system. This outcome represents an attempt to reduce the negative influence of this infection on the outcome of the transplant and on the

management of health resources, provided that the other key variables of efficacy and safety of these immunosuppression regimens are not inferior to those demonstrated by standard treatment.

2. Research plan

2.1 Study design:

This prospective, randomized, single-center clinical study was designed to compare the safety and efficacy of three immunosuppressive regimens (Group 1, SRL) single-dose r-ATG, TAC, SRL, and prednisone; (Group 2, EVR) single dose of r-ATG, TAC, EVR and prednisone; (Group 3, MCF) single dose of r-ATG, TAC, MPA and prednisone.

The study was submitted to the local research ethics committee for approval and an informed consent form will be obtained from all patients. The study will be conducted within good clinical practice in accordance with the Declaration of Helsinki. Patients who meet the inclusion and exclusion criteria will be randomized within the first 24 hours after transplantation, in a 1:1:1 ratio and stratified according to the type of donor (deceased or living). All patients will be followed for 12 months or until graft loss.

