2.4 Maintenance therapy

The first dose of all immunosuppressive drugs will be administered within the first 24 hours after graft revascularization.

Treatment group	Drug	Initial dose	Concentration (ng/ml)
Group 1, SRL (n=50)	r-ATG	3 mg/Kg IV day 1	NA
	TAC	0,05 mg/kg BID	3-5
	Sirolimus	3 mg QD	4-8
Group 2, EVR (n=50)	r-ATG	3 mg/Kg IV day 1	NA
	TAC	0,05 mg/kg BID	3-5
	EVR	1,5 mg BID	4-8
Group 3, MCF (n=50)	r-ATG	3 mg/Kg IV day 1	NA
	TAC	0,1 mg/kg BID	5-10
	MMF ou MPS	1000 mg BID	NA
		720 mg BID	NA

The primary use of other immunosuppressive drugs is prohibited. However, switching to another immunosuppressive drug is permitted both due to lack of efficacy (documented episodes of acute rejection) and the occurrence of adverse events.

At the 6 month visit, all patients who are eligible, according to pre-established criteria, will simplify the TAC and EVR dosing schedule of BID for QD, maintaining the same daily dose in a single dose to achieve blood concentrations between 3 and 5 ng/ ml.

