2.6 Study rationale

The use of a single dose of 3 mg/kg of anti-thymocyte globulin in induction therapy is currently standard in our institution, consistently providing an incidence of acute rejection of less than 10% at the end of the first year of transplantation. However, patients receiving this therapy and induction combined with standard maintenance therapy (TAC, mycophenolate, and prednisone) have a high incidence (60%) of CMV infection/disease. Using sirolimus or everolimus instead of mycophenolate may maintain efficacy for preventing acute rejection while reducing the incidence of CMV infection/disease.

Adherence to immunosuppressive treatment is one of the factors with an important influence on long-term renal graft survival (9). The incidence of non-adherence to treatment varies among different populations of kidney transplant recipients, reaching 60% in some cases. Constant education, technological facilities to alert the patient and simplification of medication dosage are strategies that can improve treatment adherence (10).

Among the maintenance immunosuppressive regimens currently available to kidney transplant recipients, none offers the possibility of once-daily administration of all drugs to facilitate adherence to treatment.

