2.8 Risks/benefits

Sirolimus or everolimus regimens may reduce the incidence of viral infections, including CMV, herpes, and polyomavirus infection. In addition, there may be a reduction in the incidence of fungal and bacterial infections, a lower incidence of

diarrhea and myelotoxicity associated with the use of MPA. On the other hand, these regimens are associated with slow recovery of renal function, higher incidence of wound complications, edema, nephrotoxicity, proteinuria, and dyslipidemia. All of these adverse reactions are associated with disproportionately high concentrations of TAC and sirolimus or everolimus.

3. Population

A sample calculation was performed for each outcome to be analyzed in this study. The complete description is in section 10. "Statistical planning".

A total of 319 patients were included in the study.

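### Section 10.1 plans on a 72% control CMV rate where section 2.6 gives 60% for the same regimen, and 42 per group, 50 per group and 319 included are not linked

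*Combined protocol and SAP*

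**What the plan says.** **Control rate.** Section 10.1 (Sample size - main study) says "we considered an incidence of 72% in the MPA group and an expected reduction of 50% (to 36%) in the experimental groups". It gives no source, period or denominator for the 72%.

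Section 2.6 (Study rationale) describes the centre's own practice: "The use of a single dose of 3 mg/kg of anti-thymocyte globulin in induction therapy is currently standard in our institution". It then reports that "patients receiving this therapy and induction combined with standard maintenance therapy (TAC, mycophenolate, and prednisone) have a high incidence (60%) of CMV infection/disease". The 60% also has no source, period or denominator. Section 2.1 defines Group 3, the control arm, as single-dose r-ATG with TAC, MPA and prednisone. That is the regimen to which the 60% refers, and the trial is single-centre.

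**Size.** With a superiority margin of 0%, section 10.1 concludes: "power of 90%, the total number of patients would be 42 in each group, considering 20% drop outs". Alpha and sidedness are not stated. The table in section 2.4 gives n=50 for each of the three groups. Section 3 (Population) reports 319 patients included. Section 3 also says "A sample calculation was performed for each outcome to be analyzed in this study" and "The complete description is in section 10". The section 10 supplied contains only the CMV calculation.

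**The concern.** The control rate is one of the two inputs that fix the sample size. The protocol gives two values for it, 12 percentage points apart, for one regimen and one endpoint at one centre. With the relative reduction held at 50%, a lower control rate gives a smaller absolute difference (30 points instead of 36) and so less power. If 42 per group was the plan, the stated 90% depends on using 72% and not the centre's own 60%.

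The second problem is traceability. The three sizes imply totals of 126 (3 x 42), 150 (3 x 50) and 319. A reader cannot tell which was planned, at what alpha, or which outcome drove it, and so cannot say what power the trial was designed to have.

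**Working it through.** **Inputs.** From section 10.1: 72% control, 36% experimental, 90% power, margin 0%, 20% dropout, 42 per group. From section 2.6: 60% control. From section 2.4: 50 per group. From section 3: 319 in total. From section 2.1: 1:1:1 allocation, so 319/3 = 106.3 per arm. Assumed: two-sided 5% for each comparison of an experimental arm with MPA, with two-sided 2.5% as a sensitivity case.

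**1. Reproduce the plan's 42.** Two proportions, unpooled variance:

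n = [p1(1-p1) + p2(1-p2)] x (z_0.975 + z_0.90)^2 / (p1-p2)^2

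- Variance term: 0.72 x 0.28 + 0.36 x 0.64 = 0.2016 + 0.2304 = 0.432.
- (1.960 + 1.282)^2 = 10.507.
- n = 0.432 x 10.507 / 0.36^2 = 35.02 evaluable per arm.
- Dropout as n x 1.2: 35.02 x 1.2 = 42.03, which is the stated 42. Dropout as n / 0.8 gives 43.8.

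**2. Replace 72% by 60% and keep the 50% reduction (60% against 30%).**

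- Variance term: 0.24 + 0.21 = 0.45.
- n = 0.45 x 10.507 / 0.30^2 = 52.5 evaluable per arm for 90% power, or 63.0 (x 1.2) to 65.7 (/ 0.8) randomised.

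**3. Power at each size in the documents.** Power = Phi( |p1-p2| / sqrt(V/n) - z_(1-alpha/2) ), where V is the variance term and n the evaluable number per arm. Each range covers the two readings of 20% dropout: randomised x 0.8 and randomised / 1.2.

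| Size | Evaluable per arm | 72% vs 36%, two-sided 5% | 60% vs 30%, two-sided 5% |
|---|---|---|---|
| 42 per group | 33.6 to 35 | 89-90% | 74-75% |
| 50 per group | 40 to 41.7 | 93-94% | 81-82% |
| 319 in total | 85.1 to 88.6 | above 99% | 98-99% |

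Worked example, 42 per group at 60% against 30%: 0.30 / sqrt(0.45/35) = 2.646; 2.646 - 1.960 = 0.686; Phi(0.686) = 0.754.

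**4. Keep the experimental rate at 36% instead (60% against 36%, a 40% reduction).** The documents do not say whether the 50% reduction or the 36% would carry over to a 60% control rate.

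- V = 0.24 + 0.2304 = 0.4704.
- With 319 in total, power is 90-91% at two-sided 5% and 84-85% at two-sided 2.5%.

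**5. Look for a link between the sizes.** No step in sections 2.4, 3 or 10.1 leads from 42 to 50 or from either to 319. Section 3 points to section 10 for the remaining calculations, and the section 10 supplied goes from the CMV calculation straight to the references.

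**The case against.** The strongest case on the other side is that the loss of power is conditional. Section 3 says in the past tense that 319 patients were included, which reads as enrolment. At that size, 60% against 30% has 98-99% power after dropout, and the fall to about 75% matters only if 42 per group was the operative size. That stands, and it makes this mainly a fault of justification and consistency. It does not make the CMV comparison safe under every reading: at 60% against 36% power is 84-85% if alpha is two-sided 2.5% per comparison.

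It is also fair that 60% may be a sound institutional figure, that 72% may be right for the trial population, and that a true reduction larger than 50% would recover power at 42 per group. The protocol gives none of these as its reason for using 72%.

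Four stronger readings are tempting, and the documents do not support them:

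- *The 42 is miscalculated.* It is not; it follows from the inputs in section 10.1 under ordinary assumptions.
- *The trial was underpowered.* That cannot be said while the operative size is unknown and 319 may be the enrolment.
- *The three sizes contradict one another.* They need not: 319 may be actual enrolment, or another outcome may have driven it. Equally, a choice of formula that happens to land near 50 or 319 would not be evidence of a link, because the documents state none.
- *The other calculations were never done.* They may lie outside the posted text. Section numbers jump from 5 to 9, section 10.1 is labelled as the main study, and the reference list holds items on topics that the text does not cover. What can be said is that the cross-reference in section 3 leads to nothing in the section 10 supplied.

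**Conclusion.** The point holds as an unreconciled planning input together with an untraceable sample size. At the protocol's own 60%, with the planned 50% reduction, 42 per group gives about 74-75% power and 50 per group 81-82%, not the stated 90%. With 319 the shortfall disappears at 60% against 30%. At 60% against 36% power stays at about 90% for two-sided 5% and falls below it for two-sided 2.5%.

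These figures rest on an alpha that the protocol does not state, on the unpooled normal approximation (chosen because it reproduces 42), on equal arms, and on 20% dropout read in either of two ways. Neither 72% nor 60% can be shown to be the right rate from the documents. The finding is that both are given, for the same regimen and endpoint, without explanation. This should be corrected, but it does not by itself put the primary comparison in doubt.

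**What to change.** - **Control rate.** In section 10.1, either use the 60% of section 2.6 and restate the power at the planned size (about 75% if that is 42 per group), or give the source of 72% and say why it differs from 60%. Section 2.6 need not change if the difference is explained.
- **Alpha.** State alpha and sidedness for SRL against MPA and for EVR against MPA.
- **Size.** Give one planned size, the same in sections 2.4, 3 and 10.1, with the calculation behind it. Label 319 as planned or actually enrolled.
- **Cross-reference.** Supply the calculations for the other outcomes in section 10, or correct the sentence in section 3.

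The cost is rewording of a few sections. If 60% is adopted, the stated power at 42 or 50 per group becomes less favourable. Restating the power, and not raising the number, means that no extra patients are needed.
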